## B. Second Modification on Treatment

Serum phosphorus level	Intervention
5.5 – 6.5 mg/dL	
Continue treatment with Debio 1347 at a current dose AND Continue sevelamer oral POWDER or tablets 2400mg three times a day
 <hr/> 
Introduce treatment with lanthanum carbonate (Fosrenol®) to 1.0g three times a day or increase to 1.5g three times a day
 <hr/> 
Reassess serum phosphorus level within 7 days

6.6-6.9 mg/dL	
Continue treatment with Debio 1347 at current dose AND Continue sevelamer oral POWDER or tablets 2400mg three times a day
 <hr/> 
Introduce treatment with lanthanum carbonate (Fosrenol®) to 1.0g three times a day or increase the dose to 1.5g three times a day
 <hr/> 
Add treatment with oral acetazolamide 250mg twice a day
 <hr/> 
Reassess serum phosphorus level within 7 days

≥ 7 mg/dL	
Hold treatment with Debio 1347 – consider dose reduction Continue sevelamer oral POWDER or tablets 2400mg three times a day
 <hr/> 
Increase treatment with lanthanum carbonate (Fosrenol®) to 1.5g three times a day AND
 <hr/> 
Add treatment with oral acetazolamide 250mg twice a day
 <hr/> 
Reassess serum phosphorus level within 7 days:
 
 
- If serum phosphorus level < 5.5 mg/dL → resume Debio 1347 with dose reduction
 

	
N.B.
 
 
- Sevelamer should be preferably taken in the mid of meals
 
- Lanthanum carbonate should be taken just after meals
 
- Sevelamer and lanthanum must be administered at least 2 hours after or 4 hours before Debio 1347
 
- Acetazolamide should be preferably taken just after breakfast and dinner
 

### C. Subsequent Modifications

Serum phosphorus level	Intervention
> 5.5 mg/dL - 6.9mg/dL	
 
• If not already done, maximize regimen to include:               
 
- Sevelamer oral POWDER or tablets to 2400mg three times a day
 
- Lanthanum carbonate (Fosrenol®) to 1.5g three times a day
 
- Oral acetazolamide 250mg twice a day
 
 
 
• If regimen already maximized, consider dose reduction (without interrupting Debio 1347 assumption)
 
 <hr/> Reassess serum phosphorus level within 7 days
≥ 7 mg/dL	<hr/> Hold treatment with Debio1347 – dose reduction needed <hr/> Maximize regimen to include: 
 
- Sevelamer oral POWDER or tablets to 2400mg three times a day
 
- Lanthanum carbonate (Fosrenol®) to 1.5g three times a day
 
- Oral acetazolamide 250mg twice a day
 
 <hr/> Reassess serum phosphorus level within 7 days: 
 
- If serum phosphorus level < 5.5 mg/dL → resume Debio 1347 with dose reduction
 

	N.B. 
 
- Sevelamer should be preferably taken in the mid of meals
 
- Lanthanum carbonate should be taken just after meals
 
- Sevelamer and lanthanum must be administered at least 2 hours after or 4 hours before Debio 1347
 
- Acetazolamide should be preferably taken just after breakfast and dinner
 

### D. General Recommendations

1. **In subjects whose serum phosphorus control improves after Debio 1347 dose reduction, de-escalation of the hyperphosphatemia treatment can be considered at the discretion of the Investigator. Subsequent to any such adjustment, serum phosphorus level should be reassessed within 7 days.**
2. **In case of subjects with hepatic or renal impairment, it is recommended not to change hyperphosphatemia treatment even in the case of Debio 1347 dose reduction.**

## Appendix F: Dermatological toxicity prophylaxis and management

These are suggested guidelines based on emerging data from studies testing FGFR inhibitors and from experience of participating Investigators and certified dermatologists. However, clinical judgment by the treating physicians and local SOC must be followed to decide which management is the best for each case of dermatologic toxicity.

### PARONYCHIA

Severity (CTCA v.4.03)	Intervention

Grade 0
	
Prophylaxis with urea 10-20% moisturizing cream twice daily
 <hr/> 
Gentle skin care recommendation for the subjects:
 
 
- Avoid repeated trauma or friction and pressure on nails and nail beds from manicuring, artificial nails, nail biting, hangnails, or removal of the cuticle
 
- Always use protective cotton gloves for fingernails and vinyl gloves for prolonged contact with water such as for dish washing
 
- Contact with detergents, toxic nail products (e.g., toluene and formaldehyde), and use of nail polish removers and hardeners should be restricted
 
- Trim nails regularly and ensure that they are straight and short, and smooth the edges with a nail file
 
- Apply topical emollients to cuticles and periungual tissues every day; nail lacquers can also be used to restrict water evaporation from the nail plate
 
- Wear cotton socks and comfortable wide-fitting footwear
 

Grade 1 Nail fold oedema or erythema; disruption of the cuticle
 
or
 
Grade 2 Localized intervention indicated ; oral intervention indicated (eg, antibiotic, antifungal, antiviral) ; nail fold oedema or erythema with pain ; associated with discharge or nail plate separation ; limiting instrumental ADL
	
Continue treatment of Debio 1347 at current dose and monitor for change in severity
 <hr/> 
Consider bacterial/viral cultures
 
Consider treatment with oral antibiotics (e.g. Cefadroxil or Ciprofloxacin 500 mg twice daily for 10-14 days) and antiseptic soaks for at least 14 days*
 <hr/> 
Reassess after 2 weeks (either by healthcare professional or subject self-report):
 
 
1. If reactions do not improve, re-consider bacterial/viral cultures and change oral antibiotics accordingly.
 


Grade 3 Surgical intervention or IV antibiotics indicated; limiting self-care ADL
	
Interrupt Debio 1347; obtain bacterial/viral cultures
 <hr/> 
Continue treatment with systemic antibiotics;
 
Consider dermatological evaluation;
 
Consider nail avulsion.
 <hr/> 
Reassess after 2 weeks:
 
 
1. If reactions worsen or do not improve, dose reduction per Principal Investigator clinical judgment may be necessary.
 
2. Treatment discontinuation should be reserved after dose reduction.
 

\*Antiseptic soaks consist of soaking fingers or toes in a solution of white vinegar in water 1:1 for 15 minutes every day. [Modified from Y. Balagula, M.E. Lacouture, and J.A. Cotliar, Dermatologic Toxicities of Targeted Anticancer Therapies. J Support Oncol 2010;8-149-161]

## HAND FOOT SYNDROME

Severity (CTCA v.4.03)	Intervention
Grade 0	Prophylaxis with urea 10-20% moisturizing cream twice daily and after every hand wash

Grade 1
 
Minimal skin changes or dermatitis (eg, erythema, oedema, or hyperkeratosis) without pain.
 
or
 
Grade 2
 
Skin changed (eg, peeling, blisters, bleeding, oedema, or hyperkeratosis) with pain; limiting instrumental ADL
	
Continue treatment of Debio 1347 at current dose and monitor for change in severity
 <hr/> 
Consider treatment with Clobetasol 0.05% cream or foam twice daily and control pain and/or inflammation with NAIDS twice daily (preferably a COX2 inhibitor such as Celecoxib 100 mg twice daily)
 <hr/> 
Reassess after 2 weeks (either by healthcare professional or subject self-report)

Grade 3
 
Severe skin changes (eg, peeling, blisters, bleeding, oedema, or hyperkeratosis) with pain; limiting self-care ADL
	
Interrupt treatment of Debio 1347 until severity decreases to grades 0-1
 <hr/> 
Continue treatment with Clobetasol 0.05% cream or foam twice daily and control pain and/or inflammation with NAIDS twice daily (preferably a COX2 inhibitor such as Celecoxib 100 mg twice daily)
 <hr/> 
Reassess after 2 weeks:
 
 
1. If reactions worsen or do not improve, dose reduction per Principal Investigator clinical judgment may be necessary.
 
2. Treatment discontinuation should be reserved after dose reduction.
 

**XEROSIS (DRY SKIN)**

Severity (CTCA v.4.03)	Intervention

Grade 0
	
Prophylaxis with urea 10-20% moisturizing cream twice daily Fragrance-free detergents and soaps

Grade 1 Covering < 10% BSA and no associated erythema or pruritus or Grade 2 Covering 10-30% BSA and associated with erythema or pruritus; limiting instrumental ADL
	
Continue treatment of Debio 1347 at current dose and monitor for change in severity
 <hr/> 
Continue moisturizer with urea 10-20% cream and consider adding a mid-potency topical steroid cream (i.e. Triamcinolone 0.1% cream or a steroid cream with equivalent potency)
 <hr/> 
Reassess after 2 weeks (either by healthcare professional or subject self-report); if reactions worsen proceed to next step

Grade 3 Covering > 30% BSA and associated with pruritus; limiting self-care ADL
	
Interrupt treatment of Debio 1347 until severity decreases to grades 0-1
 <hr/> 
Consider treatment with topical steroid cream twice a daily (e.g. Triamcinolone 0.1% cream or a steroid cream with equivalent potency)
 <hr/> 
Reassess after 2 weeks:
 
 
1. If reactions worsen or do not improve, dose reduction per Principal Investigator clinical judgment may be necessary
 
2. Treatment discontinuation should be reserved after dose reduction.
 

**ALOPECIA**

Severity (CTCA v.4.03)	Intervention

Grade 0
	
Consider prophylaxis with Minoxidil 5% daily

Grade 1 Hair loss of < 50% of normal for that individual that is not obvious from a distance but only on close inspection; a different hair style may be required to cover the hair loss but it does not require a wig or hair piece to camouflage
 
or
 
Grade 2 Hair loss of ≥ 50% of normal for that individual that is readily apparent to others; a wig or hair piece is necessary if the subject desires to completely camouflage the hair loss; associated with psychosocial impact
	
Continue treatment of Debio 1347 at current dose and monitor for change in severity
 <hr/> 
Consider dermatologic evaluation
 <hr/> 
Reassess after 2 weeks (either by healthcare professional or subject self-report)

Grade 3 NA
	
NA

## ORAL MUCOSITIS

Severity (CTCA v.4.03)	Intervention
Grade 0	NA
Grade 1 Asymptomatic or mild symptoms; intervention not indicated or Grade 2 Moderate pain; not interfering with oral intake; modified diet indicated	
Continue treatment of Debio 1347 at current dose and monitor for change in severity
 <hr/> 
Consider Dexamethasone 0.5% mouthwash three times a day.
 <hr/> 
Reassess after 2 weeks (either by healthcare professional or subject self-report); if reactions worsen or do not improve, proceed to next step.

Grade 3 Severe pain; interfering with oral intake	
Interrupt treatment of Debio 1347 until severity decreases to grades 0-1
 <hr/> 
Continue treatment with Dexamethasone 0.5% mouthwash three times a day.
 <hr/> 
Reassess after 2 weeks:
 
 
1. If reactions worsen or do not improve, dose reduction per Principal Investigator clinical judgment may be necessary
 
2. Treatment discontinuation should be reserved after dose reduction.
 

### Appendix G: Hypercalcemia treatment

Subjects with asymptomatic hypercalcemia do not require immediate treatment if the calcium level remains < 12 mg/dL (3 mmol/L). However, the subject should be advised to avoid factors that can aggravate

hypercalcemia (such as thiazide diuretics, volume depletion, prolonged bed rest or inactivity, and a high calcium diet [ $> 1000$  mg/day]).

Adequate hydration (at least 6 glasses of water per day) is recommended to minimise the risk of nephrolithiasis.

- *Moderate asymptomatic hypercalcemia (calcium between 12 and 14 mg/dL [3 to 3.5 mmol/L]):* The decision to treat with saline hydration and bisphosphonates is at the Investigator's discretion.
- *Higher concentrations of calcium  $> 14$  mg/dL (3.5 mmol/L) or the presence of symptoms requiring more aggressive therapy.* In this case, it is suggested to treat with a three-pronged approach of isotonic saline (at an initial rate of 200 to 300 mL/hour that is then adjusted to maintain the urine output at 100 to 150 mL/hour), salmon calcitonin (4 IU units/kg) and concurrent administration of zoledronic acid (4 mg IV over 15 minutes) or pamidronate (60 to 90 mg over two hours).

9.2 DATES, TIMES AND DAYS.....	16
9.3 TIMING OF ANALYSES.....	17
10 STATISTICAL ANALYSIS METHODS	17

LIST OF ABBREVIATIONS AND DEFINITIONS

Abbreviation	Definition
AE	Adverse event
AESI	Adverse event of special interest
ATC	Anatomical therapeutic chemical
AUC	Area under the concentration versus time curve
BLOQ	Below limit of quantification
BOR	Best overall response
█	█
CI	Confidence interval
C _{max}	Maximum serum concentration
CR	Complete response
█	█
CTCAE	Common terminology criteria for adverse events
CV	Coefficient of variation
DCR	Disease control rate
DOR	Duration of response
ECG	Electrocardiogram
ECOG	Eastern cooperative oncology group
eCRF	Electronic case report form
FGFR	Fibroblast growth factor receptor
FWER	Family-Wise error rate
H ₀	Null hypothesis
H ₁	Alternative hypothesis
HR	Heart rate
IMP	Investigational medicinal product
IRC	Independent review committee
ITT	Intent-to-treat
K-M	Kaplan-Meier
LOQ	Limit of quantification
MedDRA	Medical dictionary for regulatory activities
mITT	Modified ITT
NCI	National cancer institute
NE	Not evaluable
ORR	Objective response rate

Abbreviation	Definition
OS	Overall survival
PA2	Protocol amendment 2
PD	Progressive disease
PFS	Progression-free survival
█	█
PK	Pharmacokinetics
PP	Per protocol
PR	Partial response
P-R	Interval between the P and R waves
█	█
PS	Performance status
PT	Preferred term
Q1	25 th percentile
Q3	75 th percentile
QD	Once daily
█	█
QRS	Distance between the Q and S waves
QT	Interval between the Q and T waves
QTcF	QT interval corrected for heart rate using Fridericia 's formula
QTcSS	Study specific QT correction
RECIST	Response evaluation criteria in solid tumors
RR	Interval between 2 consecutive R waves
SAE	Serious adverse event
SAP	Statistical analysis plan
SD	Stable disease
SDlog	Standard deviation of the log-transformed values
SE	Standard error
SOC	System organ class
TEAE	Treatment-emergent adverse event
TNM	Tumor-Node-Metastasis
█	█
WHO-DD	World health organization drug dictionary

1 INTRODUCTION

This statistical analysis plan (SAP) describes the statistical analyses planned to be performed for the study Debio 1347-201 entitled “A Phase II basket study of the oral selective pan-FGFR inhibitor Debio 1347 in subjects with solid tumors harboring a fusion of FGFR1, FGFR2 or FGFR3”. The SAP is compliant with the study protocol version 3, dated of July 16th 2020. The SAP will be finalized prior to the database lock for the main analysis.

The rationale for Protocol Amendment 2 (PA2) was

- The results of data monitoring reviews of pooled data (Section **Error! Reference source not found.**) showed that the antitumor activity of Debio 1347 was lower than initially assumed at the time the protocol was developed. Considering that further enrolment is unlikely to substantially change the magnitude of the efficacy observed up to now, Debiopharm decided to permanently halt the enrolment in the study after consultation with the IDMC on June 10th, 2020.

After implementation of PA2:

- After consenting to PA2, on-treatment subjects will no longer be assessed for efficacy in the study, but only for safety.
- Off-treatment subjects will not be followed for disease status or survival in the study, but only for safety up to 30 days post last dose of Debio 1347.
- Subjects will complete study participation at 30 days after the last dose of Debio 1347. In the case of off-treatment subjects with >30 days and <2 years follow-up at the time of PA2 implementation, then these subjects can complete study participation immediately.

The SAP will pre-specify the statistical consideration for the analysis of study data to ensure validity of study findings and conclusions regarding study objectives.

2 STUDY OBJECTIVES

2.1 Primary Objective

The primary objective is to assess the efficacy of Debio 1347 in terms of objective response rate (ORR) in subjects with solid tumors harboring fibroblast growth factor receptor (FGFR) 1-3 gene fusion/rearrangement.

2.2 Secondary Objectives

The secondary objectives are:

1. To evaluate the efficacy of Debio 1347 in terms of duration of response (DOR), disease control rate (DCR), progression free survival (PFS) and overall survival (OS).
2. To assess the safety of Debio 1347.
3. To assess exposure-response relationships versus efficacy and safety (notably QTcF).

[REDACTED]

■ [REDACTED]

■ [REDACTED]

■ [REDACTED]

■ [REDACTED]

■ [REDACTED]

3 STUDY ENDPOINTS

In subjects enrolled late in the study, PA2 shortens the data collection period for efficacy data. After PA2 is in force, efficacy assessments and central radiological review will no longer be performed in on-treatment subjects, and off-treatment followed up for disease status and survival will no longer be performed in off-treatment subjects.

After PA2 is in force, onl for on-treatment and off-treatment subjects will be collected using standard institutional practice and local laboratory testing in accordance with the protocol study plan to support the ongoing safety assessments.

3.1 Primary Endpoint

The primary endpoint is ORR, defined as the proportion of subjects with a best overall response (BOR) of partial or complete response as centrally measured by RECIST 1.1 criteria.)

3.2 Secondary Endpoints

The secondary endpoints are:

1. DOR, defined as the time from the date of the initial partial response (PR) or complete response (CR) to date of the first documented progressive disease (PD) or death due to any cause.
2. DCR, defined as the proportion of subjects with a BOR of CR, PR or SD .
3. PFS, defined as the time from the start date of treatment to date of the first documented PD or death due to any cause.
4. OS, defined as the time from the start date of treatment to date of death due to any cause.
5. Proportion of subjects with treatment-emergent adverse events (TEAEs) assessed by the National Cancer Institute - Common Terminology Criteria for Adverse Events (NCI-CTCAE) v5.0 and proportion of subjects with serious adverse events (SAEs).
6. Debio 1347 plasma exposure (C_{trough} , area under the curve [AUC $_{\tau}$] and any other PK parameters as deemed appropriate) and relationships with efficacy and safety endpoints; Debio 1347 plasma concentration (C)-QTcF relationship based on electrocardiogram (ECG) and PK matching time-points. These relationships will be derived only if deemed appropriate, depending on the safety and efficacy outcomes and data availability.

■ [REDACTED]

■ [REDACTED]

■ [REDACTED]

■ [REDACTED]

■ [REDACTED]

■ [REDACTED]

■ [REDACTED]

■ [REDACTED]

■ [REDACTED]

■ [REDACTED]

4 STUDY DESIGN AND TREATMENT

[figure not shown]
4.1 Study Design

4.1.1 Study design before protocol amendment 2

This is a multicenter, basket, two stage, adaptive single arm Phase II study to examine the efficacy of Debio 1347 administered at the recommended Phase II daily dose of 80 mg in subjects with solid tumors harboring FGFR1-3 gene fusion/rearrangement. The study will include 3 cohorts of subjects comprising biliary tract cancer (Cohort 1), urothelial cancer (Cohort 2) and, in Cohort 3, all other solid tumor histologies not included in cohort 1 or cohort 2, such as non-small cell lung cancer (NSCLC), head and neck cancer, thyroid cancer, oral cancer, breast cancer, prostate cancer and others but excluding primary brain tumors.

Stage 1 will require 27 evaluable subjects across the three cohorts assuming an equal accrual rate per cohort. Stage 2 will require 86 evaluable subjects across all cohorts or per individual cohort depending on results of assessments scheduled at the end of Stage 1 (see Figure 1).

Figure 1 - Graphical algorithm representing study design (extracted from Cunanan et al. (2017))

Subjects will be treated with Debio 1347 once daily (QD) in 28-day cycles until the occurrence of disease progression (clinical or radiologic) or unacceptable toxicity. Subject safety (AEs) and survival will be followed-up respectively for 30 days after the last Debio 1347 dose and every 12 weeks from treatment end until death or loss to follow-up but no longer than for a total of 2 years after the last subject has discontinued treatment. Disease status will be followed-up every 12 weeks only in subjects without PD from treatment end until PD, death or loss to follow-up but no longer than for a total of 2 years after the last subject has discontinued treatment.

An Independent Data Monitoring Committee (IDMC) will be established to review safety, tolerability and efficacy data, as well as to monitor the overall conduct of the study at regular intervals. Interim analysis will also be discussed by IDMC.

The IDMC meeting schedule, purpose, roles and responsibilities will be outlined in a separate document, the IDMC Charter.

4.1.2 Study design after protocol amendment 2

The interim analysis was not conducted as planned (as detailed in section 10.8.2). Based on an initial statistical review of pooled data, the antitumor activity for Debio 1347 is lower than initially assumed at the time the protocol was developed. Debiopharm decided to permanently halt the enrollment in stage 1 of the study after consultation with the IDMC on June 10th, 2020.

The subsequent protocol amendment 2 (PA2) was implemented to modify the study design in the following ways:

- All ongoing patients (on-treatment subjects and off-treatment subjects still under follow-up) will be re-consented to PA2.
- Subjects showing clinical benefit may remain on-treatment with Debio 1347 until a condition to stop treatment is met.

- After consenting to PA2, on-treatment subjects will no longer be assessed for efficacy in the study, but only for AE, SAE and AESI as described in the pared down study plan of PA2 (**Error! Reference source not found.**).
- Off-treatment subjects will not be followed for disease status or survival in the study, but only for AE, SAE and AESI up to 30 days after the last dose of Debio 1347.
- Subjects will complete study participation at 30 days after the last dose of Debio 1347. In the case of off-treatment subjects with >30 days and <2 years follow-up at the time of PA2 implementation, then these subjects can end (i.e. complete) study participation immediately.
- Subsequent efficacy data collected through standard institutional care practice in on-treatment and off-treatment subjects will not be collected in the eCRF.
- No further IDMC meetings will be required.

4.2 Study Treatments

Subjects will receive Debio 1347 tablets at the dose of 80 mg QD from Day 1 to Day 28 in 28-day cycles until occurrence of any of the criteria described in the protocol requiring treatment discontinuation.

5 RANDOMISATION AND BLINDING

Not applicable.

6 SAMPLE SIZE

A basket two stage adaptive design will be used to assess the efficacy of Debio 1347 in terms of ORR, (Cunanan et al. 2017).

With 27 evaluable subjects in Stage 1 and 86 evaluable subjects in Stage 2, the study will have approximately 90% power to reject the null hypothesis that $ORR \leq 15\%$ when the true ORR is 30% in at least one of the baskets, using a one-sided exact binomial test at an overall significance level of 5%. The sample size for Stage 2 is for a pooled sample across baskets in case homogeneity is shown at end of Stage 1, or for one active basket taken into Stage 2 in case of heterogeneity. Sample size and design operating characteristics were determined using simulations, see Table 1.

Assuming homogeneity across baskets and a 10% drop out, the study would enroll approximately 125 subjects.

If homogeneity is declared at the interim analysis, 86 participants across three cohorts will be enrolled in stage 2. Otherwise, 86 participants will be enrolled in stage 2 in each of the cohorts continuing into stage 2.

Table 1 - Power and expected sample size based on 1000 simulations using Cunanan et al. (2017) algorithm

Assumed ORR of 15% for inactive cohorts and 30% for active cohorts	Number of truly active cohorts			
	0 Active	1 Active	2 Active	3 Active
Marginal Power				
FWER	5%	16%	39%	NA
Power 1 active cohort	3%	64%	88%	92%
Power 2 active cohorts	3%	15%	87%	93%

Nt period	Power 3 active cohorts	4%	15%	39%	93%
Expected sample size		111	148	165	161
% Homogeneity rejected at end of stage 1		38%	54%	57%	46%
Cohort 1 continuing to stage 2		25%	52%	54%	42%
Cohort 2 continuing to stage 2		26%	36%	53%	42%
Cohort 3 continuing to stage 2		24%	35%	35%	42%
Homogeneity accepted at end of stage 1		62%	46%	43%	54%
Continuing to stage 2		47%	41%	42%	54%

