### 11.1. Sample Size

A basket two stage adaptive design will be used to assess the efficacy of Debio 1347 in terms of ORR. With 27 evaluable subjects in Stage 1 and 86 evaluable subjects in Stage 2, the study will have approximately 90% power to reject the null hypothesis that  $ORR \leq 15\%$  when the true ORR is 30% in at least one of the baskets, using a one-sided exact binomial test at an overall significance level of 5%. The sample size for stage 2 is for a pooled sample across baskets in case homogeneity is shown at end of Stage 1, or for one active basket taken into Stage 2 in case of heterogeneity. Sample size and design operating characteristics were determined using simulations.

Assuming homogeneity across baskets and a 10% drop out the study would enroll approximately 125 subjects.

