10.8 Interim Analyses

10.8.1 Planned interim analysis

This study will have IDMC analyses as described in IDMC Charter with focus on study safety, drug tolerability as well as efficacy.

As a part of IDMCs, an interim analysis will be conducted at end of Stage 1 to assess ORR homogeneity across baskets as well as futility. The testing will be conducted as per the schema provided in Figure 1.

The interim analysis will be performed at end of Stage 1 on the first 27 evaluable subjects i.e. subjects in the ITT who have at least 1 post-baseline tumor assessments or progressed.

Every effort will be made to ensure equal accrual rates between cohorts during Stage 1. In case of unequal accrual rates during stage 1, the interim analysis will be conducted when the slowest enrolling cohort will have a minimum of 4 evaluable subjects and the study has a minimum of 27 evaluable subjects with a maximum of 13 evaluable subjects in any of the other cohorts.

A feasibility assessment will be evaluated prior to assessment of homogeneity to ensure the recruitment feasibility in the targeted population. One or more cohorts may be stopped prematurely as a result of the feasibility assessment. The homogeneity will be assessed by comparing, across cohort, the ORR as assessed locally by investigator at the time of the data cut-off. ORR to be used in the homogeneity assessment will be defined as the proportion of subject with a BOR of confirmed or unconfirmed CR or PR as locally assessed by the investigator. The BOR will be derived using all disease assessments performed locally by investigator prior to the data cut-off. The homogeneity assessment will be performed by comparing the observed p-value for the Fisher’s exact test for 3x2 contingency tables to the pre-defined cut off value of 0.5. Homogeneity assumption will be rejected if the p-value generated is below 0.5. The cut-off value was determined as part of the simulations for sample size determination (see Section 6).

A futility assessment will be performed after the homogeneity assessment. Futility stopping rules are described in Table 5.

Table 5 - Futility stopping rules

Homogeneity assessment	Futility assessment sample	Futility stopping rule
Homogeneity met	All cohorts combined on first 27 evaluable subjects across cohorts	Stop study for futility if less than 3 responders If 3 or more responders, continue to Stage 2 and enroll the remaining subjects across all cohorts.

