13.4.3 Estimation of FWER and Marginal Power

The trial design will be simulated 100000 times in order to gain sufficient data to calculate the measures below:

- Power: Probability of rejecting 15% in each cohort or in all cohorts combined.
- FWER: Probability of H_0 in any inactive cohort or in all cohorts combined.
- % of heterogeneity: Probability of heterogeneity case
- Non-Futility: Probability of stopping in each cohort or stop the study
- Expected Sample Size:

$$EN = \sum_{k=1}^K n_{1k} + \sum_{k \in K^*} n_{2k} \Pr(r_{sk} \geq 1 | \text{heterogeneous design path}) \Pr(\text{heterogeneous design path}) \\ + N_2 \Pr(r_C \geq 5 | \text{homogeneous design path}) \Pr(\text{homogeneous design path})$$

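### The stated power of about 90% for at least one active basket is not what the design delivers: SAP Table 1 gives 64% when exactly one basket is active

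*SAP*

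**What the plan says.** Protocol section 11.1 and the synopsis say that with 27 evaluable subjects in Stage 1 and 86 in Stage 2 "the study will have approximately 90% power to reject the null hypothesis that" the ORR is at most 15%. SAP section 6 makes the same claim. The condition is the same in all three places: the power holds "when the true ORR is 30% in at least one of the baskets, using a one-sided exact binomial test". The next sentence describes the Stage 2 size as being for a pooled sample under homogeneity "or for one active basket taken into Stage 2 in case of heterogeneity".

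SAP section 6 then points to Table 1 for the operating characteristics. In the row "Power 1 active cohort" the entry for one truly active cohort is 64%. With two active cohorts the entries are 88% and 87%; with three they are 92%, 93% and 93%. The row "Homogeneity rejected at end of stage 1" shows 54% with one active cohort. The Protocol does not carry this table.

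On Stage 2 size under heterogeneity, SAP section 6 says: "Otherwise, 86 participants will be enrolled in stage 2 in each of the cohorts continuing into stage 2".

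**The concern.** At least one active basket covers one, two or three, and power is lowest with exactly one. A single figure attached to that condition should therefore hold in the one-active case. By the SAP's own table it does not, by 26 points.

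In a basket trial, activity confined to one tumour type is a central scenario. A reader of the Protocol, who has no table to correct the sentence, takes about 90% as the chance of detecting it. In SAP section 6 the sentence contradicts the table it cites.

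With enrolment stopped, what is at stake is the recorded design justification, and how sensitive the trial is later said to have been to activity in a single cohort.

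**Working it through.** **Inputs.** ORR is 15% in inactive cohorts and 30% in active ones (SAP Table 1). Stage 1 has 27 evaluable subjects with 4 to 13 per cohort. Heterogeneity is declared if the 3x2 Fisher exact p-value is below 0.5. The pooled path continues with 3 or more responders; under heterogeneity a cohort continues with 1 or more (SAP 10.8.1). Stage 2 adds 86 pooled, or 86 per continuing cohort (SAP 6). The final test is one-sided exact binomial at 5% pooled, or 5% divided by the number of non-futile cohorts (SAP 10.2.1.1).

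**Reading Table 1.** The three power rows behave as cohorts 1, 2 and 3: in the one-active column they read 64%, 15%, 15%. The active cohort's power is therefore 64%. Its Monte Carlo standard error is √(0.64 × 0.36 / 1000) = 0.015, so a gap of 26 points is not simulation noise.

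**Reproducing Table 1.** I enumerated all Stage 1 outcomes exactly, first at 9/9/9 and then as a multinomial-weighted average over all splits of 27 with 4 to 13 per cohort (equal accrual rates assumed; pooled Stage 2 split 29/29/28).

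| Truly active cohorts | Table 1 power | 9/9/9 | Averaged | Homogeneity rejected: Table 1 | Averaged |
|---|---|---|---|---|---|
| 1 | 64% | 60.7% | 66.5% | 54% | 54.3% |
| 2 | 87-88% | 85.4% | 85.3% | 57% | 55.4% |
| 3 | 92-93% | 92.8% | 91.4% | 46% | 44.2% |

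Across single Stage 1 splits the one-active power runs from 59.0% to 71.7%. Table 1 is credible; the sentence is not.

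**Where the one-active power goes.** Power = P(het) × power given het + P(hom) × power given hom.

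- Averaged: 0.543 × 0.904 + 0.457 × 0.381 = 0.491 + 0.174 = 0.665.
- At 9/9/9: 0.432 × 0.929 + 0.568 × 0.362 = 0.401 + 0.206 = 0.607.

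Table 1 prints no power by path, but an approximate split follows. Inactive cohorts are rejected 15% of the time, and the enumeration puts about 96% of that in the pooled test. So about 15 points come from the pooled path (15/46 = 33%) and 64 − 15 = 49 from the heterogeneous path (49/54 = 91%). When homogeneity is declared, the active basket is pooled with two inactive ones and power drops to about one third.

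**Expected sample size in Table 1.** Under the stated sizes, expected N = 27 + 86 × (sum of the three cohort continuation rates + pooled continuation rate).

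| Active | Sum of rates | 27 + 86 × sum | Printed | Printed − 86 × sum |
|---|---|---|---|---|
| 0 | 0.25 + 0.26 + 0.24 + 0.47 = 1.22 | 131.9 | 111 | 6.1 |
| 1 | 0.52 + 0.36 + 0.35 + 0.41 = 1.64 | 168.0 | 148 | 7.0 |
| 2 | 0.54 + 0.53 + 0.35 + 0.42 = 1.84 | 185.2 | 165 | 6.8 |
| 3 | 3 × 0.42 + 0.54 = 1.80 | 181.8 | 161 | 6.2 |

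Rounding explains at most 4 × 0.005 × 86 + 0.5 = 2.2. The remainder is nearly constant at 6 to 7 where the Stage 1 term of 27 should be. The averaged enumeration gives 135.7/167.4/181.9/177.1, also well above the printed row.

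The formula in SAP 13.4.3 uses a pooled cut-off of 5 responders, whereas Table 5 says "If 3 or more responders, continue to Stage 2 and enroll the remaining subjects across all cohorts". A cut-off of 5 would lower expected N by about 21/12/6/3, which is not constant, so it does not explain Table 1.

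**Tables 8 and 9.** Printed minus 86 × rates is 20.0/16.9/11.9/6.7 and 20.1/14.6/9.2/7.3. This gap varies by scenario, and the simulation behind it states other inputs (a pooled maximum of 90 in 13.4.2.1, but 86 in 13.5). With 90 pooled the remainders are 19.7/16.4/10.9/5.0 and 19.7/13.9/8.0/5.0, so the 90 does not account for it either.

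**The case against.** **The sentence may mean the heterogeneous path.** The sentence that follows it mentions one active basket under heterogeneity, and conditional power there is indeed about 90-93%. But that sentence explains the Stage 2 size. The power claim carries no such condition, and the path occurs in only 54% of one-active trials.

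**Power might mean rejecting any null.** With one active basket this gives 60.8% at 9/9/9 and 66.3% over a sample of random Stage 1 allocations, so it does not help.

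**The SAP also reports 84.0% (Table 8) and 83.1% (Table 9) with one active cohort.** True, and any restated figure should name its interim rule. Both tables add or substitute a posterior-probability criterion, which SAP 10.8.1 offers the IDMC as supportive information, and both remain below 90%.

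**The cause of the expected-N discrepancy is not uniquely identified.** This stands in part. Other combinations also fit the printed row within rounding, for example a constant of 20 with 84 per cohort and 62 pooled, or 12 with 82 for both. A wrong Stage 1 term is the simplest explanation under the stated sizes. However, the continuation rates depend only on Stage 1, so for the design as stated Table 1's own rates imply about 132/168/185/182, whatever the code used.

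**The study is closed to enrolment and the report will be abbreviated.** This limits the consequence, but the correction is cheap and the report may repeat the claim.

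**Conclusion.** The concern holds. For exactly one active basket the documents claim about 90% power; the SAP's own table gives 64%, and enumeration gives 61% to 67% depending on how Stage 1 accrual splits. None of the readings examined brings the unconditional one-active power to 90%. The enumeration rests on the SAP's stated rules and, for the averaged figure, on equal accrual rates; the contradiction between sentence and table needs neither.

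Separately, Table 1's expected-sample-size row is about 20 to 21 subjects too low for the stated stage sizes. Tables 8 and 9 have an expected-N inconsistency of a different pattern and need their own check.

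This should be fixed, with high confidence. It does not affect any planned analysis or patient number.

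**What to change.** 1. In SAP section 6, Protocol section 11.1 and the synopsis, replace the single figure with power by number of truly active baskets from Table 1: 64% with one, 87-88% with two, 92-93% with three, under the Fisher homogeneity rule. If the heterogeneous path was meant, say so and give its probability (54% with one active basket). Carry the same wording into the clinical study report. If no further protocol amendment is planned, the SAP and the report are enough.
2. Check the expected-sample-size code behind Table 1. If it confirms the stated stage sizes, leave those sizes unchanged and correct the row to about 132/168/185/182. In the same check, align the pooled responder cut-off in the SAP 13.4.3 formula (5) with Table 5 (3).
3. Reconcile the expected-N rows of Tables 8 and 9 separately, and state whether the pooled Stage 2 size there was 86 or 90.

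The cost is wording in three places, one table row and a check of existing simulation code. The stated power becomes less favourable. No extra patients are needed and no planned analysis changes.
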